5.5.4 Instructions for prescribing and taking study treatment

The study drugs (fingolimod 0.5-mg and 0.25-mg capsules and glatiramer acetate 20 mg) will be dispensed at the randomization visit (Visit 2). Drug will then be dispensed at scheduled Visits 3, 4, 5, and 6.

At Visits 2, 3, 4, 5, and 6, patients randomly assigned to fingolimod 0.25 mg or 0.5 mg will receive a bottled supply of oral medication containing a sufficient number of capsules until their next scheduled visit. At Visits 2, 3, 4, 5, and 6, patients randomly assigned to glatiramer acetate will receive a package containing a sufficient number of prefilled syringes to last until their next scheduled visit.

The fingolimod study drug needs to be taken once a day with or without food. Glatiramer acetate needs to be injected subcutaneously once a day. All study drugs should be administered preferably at the same time each day.

Site personnel will need to provide training to the patients or caregivers on the correct procedure for administration of SC injections. A patient leaflet will be provided with each supply of study drug. The patient leaflet describes information related to the study drug including: storage information, precautions, and instructions for administering SC injections. This information should be reviewed with the patients to ensure that they understand the correct procedure.

Once the eligibility of a patient for entry into the Treatment Period has been confirmed based on the study inclusion/exclusion criteria, the site will contact the IVRS to obtain a randomization number to identify study drug. Before administration of the first dose of the study drug, the investigator should reconfirm a list of concomitant medications taken by the patient.

The first dose of study drug is administered at the randomization visit (Visit 2). The treating physician will monitor the first dose intake in the clinic for at least 6 hours or longer if discharge criteria are not met in those patients receiving oral study drug (fingolimod) (see Section 5.5.5 for guidance for monitoring of patients taking their first dose of the study drug). Patients receiving injectable study drug do not require prolonged monitoring in the clinic after the first dose.

Throughout the study, careful planning of patient visits is required to make sure that the patients will have enough study drug to last until the next scheduled visit.

The investigator and study personnel should promote compliance by instructing the patient to take the study drug exactly as prescribed and by stating that compliance is necessary for the patient's safety and for the validity of the study. The patient should be instructed to contact the site if he or she is unable for any reason to take the study drug as prescribed.

All doses prescribed and dispensed to the patient and all dose interruptions during the study will be recorded in the IVRS and drug administration record in the eCRF.

5.5.5 Guidelines for monitoring patients taking their first dose of fingolimod

The patient will stay at the site for a minimum of 6 hours after the first dose of fingolimod to be monitored for signs and symptoms of bradycardia. All fingolimod patients will have an ECG performed prior to dosing and at the end of the 6-hour monitoring period. (Glatiramer acetate patients will have a single ECG during the randomization visit.) The treating physician is responsible for monitoring the patient following the first intake of fingolimod, as well as managing bradycardia symptoms should they occur. He or she must review vital signs during the 6-hour monitoring, post-dose ECG and assess discharge criteria at 6 hours after dosing.

Baseline or predose ECG should be provided by the site and be available for comparison to the postdose ECG in order to determine if discharge criteria are met.

Heart rate and blood pressure should be measured before the first dose of fingolimod, then every hour for at least 6 hours thereafter (by the treating physician or an assisting nurse). Blood pressure will be measured in the supine position and then the standing position at each time point. When obtaining the predose heart rate before the first dose, the patient should be allowed to rest in the supine position for 5 minutes before taking the heart rate. The heart rate and blood pressure measurements should be repeated twice to produce 3 baseline readings in the supine position for both heart rate and blood pressure (before the first dose of fingolimod only). Heart rate and blood pressure will then be measured in the same manner (i.e., 3 baseline readings) with the patient in the standing position before the first dose of fingolimod. For comparison to the postdose heart rate values, the lowest predose supine value and lowest predose standing value of heart rate should be used. Patients should receive the first dose of fingolimod before 12:00 PM (noon) in the outpatient setting.

Patients may be discharged after 6 hours ONLY if ALL of the following criteria are met:

- supine heart rate must be at least 45 beats per minute
- heart rate must not be the lowest hourly value measured during the observation period (which would suggest that nadir may not have been reached)
- patients must have no symptoms associated with decreased heart rate or must not have received treatment for bradycardia
- ECG at 6 hours after dosing should not show any new significant abnormalities (e.g., onset second-degree or third-degree AV block, QTc ≥500 msec) other than sinus bradycardia, that were not also observed at the patient's predose ECG

If the discharge criteria listed above are not met after 6 hours, observation must be continued until symptoms resolve.

If a patient requires treatment for bradycardia/bradyarrhythmia during the first dose observation, the patient should be monitored overnight, and the 6-hour monitoring procedure should be repeated for the second dose of study drug.

If a patient experiences a QTc interval greater than or equal to 500 msec at 6 hours after the first dose, the patient should be monitored overnight, and the 6-hour monitoring procedure should be repeated for the second dose of study drug.

Patients with some pre-existing conditions (e.g., ischemic heart disease, history of myocardial infarction, congestive heart failure, history of cardiac arrest, cerebrovascular disease, uncontrolled hypertension, history of symptomatic bradycardia, history of recurrent syncope, severe untreated sleep apnea, AV block, sinoatrial heart block) may poorly tolerate the fingolimod-induced bradycardia, or experience serious rhythm disturbances after the first dose of fingolimod. Prior to treatment with fingolimod, these patients should have a cardiac evaluation by a physician appropriately trained to conduct such evaluation, and, if treated with fingolimod, should be monitored overnight with continuous ECG in a medical facility after the first dose.

Since initiation of fingolimod treatment results in decreased heart rate and may prolong the QT interval, patients with a prolonged QTc interval (>450 msec males, >470 msec females)

before dosing or during a 6-hour observation period, or at additional risk for QT prolongation (e.g., hypokalemia, hypomagnesemia, congenital long-QT syndrome), or on concurrent therapy with QT-prolonging drugs with a known risk of torsades de pointes (e.g., citalopram, chlorpromazine, haloperidol, methadone, erythromycin) should be monitored overnight with continuous ECG in a medical facility.

Experience with fingolimod is limited in patients receiving concurrent therapy with drugs that slow heart rate or AV conduction (e.g., beta blockers, heart rate lowering calcium-channel blockers such as diltiazem or verapamil, or digoxin). Because the initiation of fingolimod treatment is also associated with slowing of the heart rate, concomitant use of these drugs during fingolimod initiation may be associated with severe bradycardia or heart block. The possibility of switching to drugs that do not slow the heart rate or AV conduction should be evaluated by the physician prescribing these drugs before initiating fingolimod. Patients who cannot switch should have overnight continuous ECG monitoring after the first dose.

In addition to protocol mandated safety assessments and monitoring procedures, additional assessments may be required as per local prescribing information and should be followed accordingly.

Patients should have written instruction on when to return to clinic and a 24-hour contact phone number to call in the event of any new or warranted symptoms (e.g., chest pain, dizziness, palpitations, syncope, nausea, vomiting). Patients should be instructed not to drive on the same day after the first dose of fingolimod administration.

Recommendations for management of bradycardia

Prior to the administration of study drug, if, in the opinion of the investigator, the patient's cardiovascular condition or medical history carry a significant risk for study participation, the patient should not be enrolled in the study, and the advice of a cardiologist should be sought.

Atropine (SC or IV) is recommended as the first line treatment of bradycardia, up to a maximum daily dose of 3 mg.

Furthermore, the common guidelines for treatment of bradycardia (e.g., ACLS guidelines) should be followed as appropriate:

- In case of clinical symptoms or hypotension, administration of atropine 1 mg, repeated administration in 3-5 minutes
- If heart rate and/or blood pressure remains unresponsive, consider administration of dopamine drip 5-20 ug/kg/min or epinephrine drip 2-10 ug/min
- Performance of transcutaneous pacing may also be considered

In the setting of decreased blood pressure, isoproterenol should be avoided/used with caution.

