dose of fingolimod, macular edema, hypertension, dyspnea, bronchitis, and diarrhea. The AEs most prominently associated with fingolimod treatment (eg, liver enzyme elevations, bradycardia, and macular edema) appeared to show a dose response. There were no AEs that appeared to be specifically related to long-term treatment with fingolimod.

- In general, the AE profile of fingolimod in MS patients did not depend on gender, age, or previous treatment with disease-modifying drugs. The only exception was liver enzyme elevations, which were more frequent in male patients than in female patients treated with fingolimod.
- The overall incidence of infections, including serious infections, was similar in the fingolimod treatment groups and the comparator arms (IFN or placebo) in both completed Phase III studies. A slightly higher frequency of lower respiratory tract infections (primarily bronchitis) was observed in fingolimod-treated patients, with an apparent dose effect. The current data showed no clear relationship between lymphocyte count and the incidence of infections on fingolimod treatment.
- The accumulated data from the MS program do not show an association of fingolimod therapy with the development of malignancies. In the FREEDOMS study, more cancers were seen in the placebo group than in the treated groups. Incidence estimates for various forms of skin cancer (and other malignancies) from pooled safety data are comparable between treatment groups and placebo. There appears to be no increased risk with greater duration of exposure (Kappos et al., 2010).
- Initiation of fingolimod treatment has been associated with atrioventricular (AV) conduction delays usually as first-degree AV blocks (prolonged PR interval on electrocardiogram [ECG]). Second-degree AV blocks, usually Mobitz Type I (Wenckebach), have been observed in less than 0.5% of patients receiving fingolimod 0.5 mg in clinical trials. The conduction abnormalities typically were transient, asymptomatic, usually did not require treatment, and resolved within the first 24 hours on treatment.
- Data on the safe use of fingolimod in pregnancy or with breast-feeding are limited, although preclinical data suggest risk to the fetus and newborn is possible.

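### Protocol 5.5.5 ends extended first-dose observation when symptoms resolve, which conflicts with its own discharge list for a patient who fails that list without symptoms

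*Protocol*

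**What the plan says.** Protocol 5.5.5 keeps fingolimod patients at the site for at least 6 hours after the first dose and watches them for signs as well as symptoms of bradycardia. The treating physician must "assess discharge criteria at 6 hours after dosing". The gate is strict: "Patients may be discharged after 6 hours ONLY if ALL of the following criteria are met". The list has four items: a supine heart rate of at least 45 beats per minute; a heart rate that is not the lowest hourly reading so far; an item on bradycardia symptoms or treatment; and an ECG item, "ECG at 6 hours after dosing should not show any new significant abnormalities", which gives new second- or third-degree AV block and QTc of 500 msec or more as examples.

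The next sentence sets the end of extended observation: "If the discharge criteria listed above are not met after 6 hours, observation must be continued until symptoms resolve".

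Two special rules follow. One begins "If a patient requires treatment for bradycardia/bradyarrhythmia during the first dose observation, the patient should be monitored overnight" and the other "If a patient experiences a QTc interval greater than or equal to 500 msec at 6 hours after the first dose". Each calls for overnight monitoring and a repeat of the 6-hour procedure at the second dose. Section 5.5.4 separately says that clinic monitoring runs past 6 hours when the discharge criteria are unmet, but gives no end point. Section 5.5.6 applies a similar procedure when fingolimod is restarted after certain interruptions.

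**The concern.** The list decides who stays, and it does so mostly on signs. The sentence that decides when they may leave speaks only of symptoms. A patient who feels well but has a rate of 42, a rate still falling, or a new AV block on the tracing fails the list, and the stated end point then gives the site nothing to work with. Taken literally, it is either met already at hour 6 or has no meaning.

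At stake is consistent handling of Day 1 cardiac safety. Two sites could treat the same patient differently, one holding until the heart rate and ECG recover and the other relying on the absence of symptoms. The plan expects such patients: SAP 8.8.1 says that bradycardia without symptoms or need for treatment is recorded on the adverse event form.

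**Working it through.** No sample size, power or error-rate figure is involved, so the check sets the texts side by side.

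**Step 1. Each discharge item against the stated end point (5.5.5).**

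| Item | Can fail with no symptoms and no treatment? | Does symptom resolution fit as an end point? | Own overnight rule? |
|---|---|---|---|
| Supine rate at least 45 | Yes | No | No |
| Rate not at its hourly lowest | Yes | No | No |
| Symptoms or treatment | No | Yes, for symptoms | Yes, if treated |
| ECG: new second- or third-degree AV block | Yes | No | No |
| ECG: QTc 500 msec or more | Yes | No | Yes |

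Three kinds of failure are left with neither a fitting end point nor a rule of their own: low rate, rate at its lowest, and new AV block.

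**Step 2. The other overnight rules in 5.5.5.** These cover listed pre-existing conditions, QTc above 450 msec (males) or 470 msec (females), other QT risks, and patients who cannot be switched from rate-slowing drugs. AV block appears among them only as a condition present before dosing. An otherwise low-risk patient with one of the three failures falls under none of them.

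**Step 3. Whether the gate supplies the missing end point.** It can be read as governing release at any time from hour 6 onward, in which case the patient stays until the list is met. It can also be read as governing release at hour 6 only, with "If the discharge criteria listed above are not met after 6 hours, observation must be continued until symptoms resolve" governing afterwards. Section 5.5.4 favours the first reading. Even so, that reading does not work as written for the ECG item, which refers to the tracing at 6 hours. Taken literally, a normal tracing at hour 8 does not change the 6-hour result. Assessment is placed at 6 hours, and neither re-assessment nor a repeat ECG is stated.

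**Step 4. Other text that might close the gap.** SAP 3.8.4 summarises Day 1 ECGs taken after 6 hours if there are any, and SAP 8.8.3 records whether extended monitoring was needed; neither requires an ECG or sets an end point. Protocol 7.1 governs follow-up of adverse events, not release from the clinic. Local prescribing information may add assessments, but its content is not in the documents.

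**Step 5. Size.** Protocol 1.1 says that second-degree AV blocks "have been observed in less than 0.5% of patients receiving fingolimod 0.5 mg in clinical trials". SAP section 10 gives 352 patients randomised to 0.5 mg, so that figure corresponds to fewer than 0.005 × 352 = 1.76 patients. This does not measure the affected group. Block on the 6-hour ECG without symptoms or treatment is only part of it, while heart-rate failures come on top. The documents give no rate for the heart-rate items, for third-degree block, or for the 0.25 mg dose.

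**The case against.** The strongest reply is that a site would have to disregard two instructions to send such a patient home. The gate demands that all items be met, and 5.5.4 ties the length of monitoring to the discharge criteria. Holding a patient until criteria are met implies checking them again. The physician must also review vital signs and the post-dose ECG, and patients leave with written return instructions and a 24-hour telephone number. This largely stands. It shows the probable intent and makes early release unlikely. It does not remove the conflict, because the only sentence that names an end point names one that does not fit.

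A reader might infer more than the documents support, in four ways:

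- **That 5.5.5 permits release with a rate below 45 or a new AV block.** It does not plainly do so; the gate and 5.5.4 point the other way.
- **That symptom-free second- or third-degree block is shown to be typical.** Section 1.1 does say "The conduction abnormalities typically were transient, asymptomatic, usually did not require treatment, and resolved within the first 24 hours on treatment", but it is describing AV conduction delays that were usually first-degree, and first-degree block is not among the list's examples.
- **That a treated patient could never later satisfy the third item.** The item joins absence of symptoms and absence of treatment with *or*, so on its letter a treated patient who becomes symptom-free meets it.
- **That Amendment 2 opened the gap by mistake when it deleted an overnight rule for bradycardia unresolved at 6 hours.** The amendment log calls the deleted paragraph erroneous. It is superseded text and serves only as background.

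**Conclusion.** The point holds as a conflict between instructions. For an untreated, symptom-free, otherwise low-risk patient who fails the 6-hour list on heart rate or on new second- or third-degree AV block, the stated end of observation disagrees with the discharge gate and with 5.5.4. In addition, the ECG item is fixed to the 6-hour tracing and no repeat is required.

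The number of such patients is probably small, but the documents do not allow it to be estimated. The below-0.5% figure covers second-degree block on one dose in earlier trials and does not bound the total. The conclusion rests on the wording alone and assumes no particular event rate. It is a minor safety-wording correction. No endpoint, analysis set or analysis is affected.

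**What to change.** Replace the sentence in 5.5.5 with:

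> If any discharge criterion is not met at 6 hours, observation must be continued, with or without symptoms, until all discharge criteria are met on the latest readings, including a repeat 12-lead ECG if the 6-hour ECG criterion was not met. Patients treated for bradycardia, or with QTc ≥500 msec at 6 hours, follow the overnight rules below.

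The second sentence keeps the existing overnight rules in force and avoids leaning on the ambiguous symptoms-or-treatment item. Whether a low rate or new AV block that persists should lead to overnight continuous ECG is a clinical decision for the sponsor's cardiac safety advisers and is separate from this correction.

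The cost is one replaced passage, or a clarification letter to sites, plus a repeat ECG and longer observation for the few patients concerned. No SAP change is needed. SAP section 10 reports early termination and a final randomised number, so the change would have helped while patients were being started or restarted. It now matters mainly for any protocol that reuses this text.

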5.5.6 Permitted dose adjustments and interruptions of study treatment

Dose adjustments will not be allowed; however, drug interruptions will be allowed based on the judgment of the investigator. If an investigator determines that study drug should be stopped, then the SC injections or oral capsules, respectively, need to be stopped. Conditions or events that may lead to study drug interruptions based on investigator judgment and overall clinical assessment are:

- SAE
- emergency medical condition or unplanned hospitalization involving the use of prohibited medications (Section 5.5.9)
- abnormal laboratory value(s) or abnormal test or examination result(s) (e.g., ECG values, ophthalmic findings). See Appendix 3 and Appendix 4 for guidance on monitoring of patients with specific test abnormalities
- hypersensitivity to the study drug
- patient noncompliance
- vaccination

The 6-hour monitoring procedure when restarting study drug is mandatory in the following cases:

- the treatment lasted for 14 days or less and was interrupted for 1 day or more, or
- the treatment lasted for more than 14 days and less than 29 days and was interrupted for more than 7 consecutive days, or
- the treatment lasted for 4 weeks or more and was interrupted for more than 14 consecutive days.

Should a patient randomized to one of the fingolimod treatment arms interrupt the study drug as described above and should the investigator decide to reinitiate treatment with the study drug, the first dose intake at restart must take place at the study site to ensure at least 6-hour monitoring by the treating physician in a similar manner as the first intake of the study drug (see for guidelines for monitoring of patients taking their first dose of the study drug in Section 5.5.5).

A reason for the interruption of treatment and dates of interruption should be documented in the source documents as well as in the dosage administration eCRF.

5.5.7 Recommendations on treatment of multiple sclerosis relapse

A standard course of intravenous corticosteroids (methylprednisolone) on an inpatient or outpatient basis is allowed for treatment of relapses as clinically warranted. Steroid treatment should consist of 3 to 5 days and up to 1000 mg methylprednisolone/day.

Standard-of-care procedures will be followed during treatment of relapses.

Use of any oral tapering is not permitted.

The use of steroid therapy should be recorded in the use of steroids for treatment of relapses eCRF. Refer to Section 6.4.3 for the instruction on conduct of the study MRI during relapse and steroid treatment.

Investigators should consider the added immunosuppressive effects of corticosteroid therapy and increase vigilance regarding infections during such treatment and in the weeks following administration.

Should a patient show evidence or suspicion of infection, please refer to the guidance on monitoring of patients with infections outlined in Appendix 3.

Should a patient develop any neurological symptoms or signs, unexpected for MS in the opinion of the investigator or accelerated neurological deterioration, the investigator should immediately schedule an MRI and follow the guidance on monitoring of patients with symptoms or signs of neurological deterioration inconsistent with MS outlined by Appendix 3. Steroids should not be taken before conducting the unscheduled MRI.

